5.0 STUDY & SUBJECT PROCEDURES

5.1 RECRUITMENT METHODS

Study Groups / subjects	Type of interaction	When	How	By whom	Materials	Procedures under consent or PHI waiver for recruitment
AIM 1. PROCESS EVALUATION						
SAVAHCS clinicians (Primary)	Interview/ focus group	Upon IRB approval,	Obtain list of clinicians from dept. Chiefs by	Coordinator, qualitative researchers	Email to clinicians ([name] Nudge Provider)	Recruitment waiver not applicable

Care, Cardiology)		beginning of study	email; email and message clinicians to participate.	on study staff, PI	email request) and ICF	because VA employee names/emails are public record. Interested subjects will sign ICF with VA electronic signature.
	Receive nudge interventions (alerts and emails)	N/A	N/A	N/A	N/A	N/A (Clinicians identified by reviewing patient charts via patient PHI – see PHI recruitment waiver chart review)
	Questionnaires	After nudge	Email provided to clinicians who received a nudge	Study coordinator	Email to clinicians	Waiver of documentation of informed consent
SAVAHCS Veteran and Family Advisory Panel	Focus group	We will attend a SAVAHCS Patient and Family Advisory Panel virtual meeting	Email / message SAVAHCS coordinator to get on meeting agenda	Coordinator, qualitative researchers on study staff, PI	Email to Advisory Council	Waiver of documentation of informed consent (no recording)
Aim 2 NUDGE EFFECTIVENESS						
SAVAHCS Patients with HF	Data collection only / chart review	Daily review of VA PBM dashboard	VA PBM website	Coordinator, study staff, PI	N/A	PHI waiver for recruitment

Aim 1. PROCESS EVALUATION

SAVAHCS clinicians (Primary Care, Cardiology). The study staff will provide information to introduce the project to the Primary Care and Cardiology providers during a routine staff meeting. The study staff will also contact Primary Care and Cardiology leadership to provide a list of all clinicians in each department. We will then email and/or Teams message clinicians to invite them to be interviewed. Informational handout will be sent via email that will include who to contact if s/he is interested in participating in the interviews and/or focus groups. Contacted up to three (3) times.

Questionnaire links will be emailed to all clinicians who received nudges. Those who wish to participate, will click on the link within the email. The questionnaire is voluntary and confidential. Contacted up to three (3) times.

SAVAHCS Veteran and Family Advisory Panel.

The study team will email/message the Advisory Panel coordinator to ask permission to be placed on the monthly Panel virtual meeting agenda. The study team will introduce the study objectives and explain that no individually identifiable data will be collected, only general study feedback.

Aim 2. NUDGE EFFECTIVENESS. A waiver of informed consent and PHI waiver are requested to review patient charts. The study staff will review the Pharmacy HF Dashboard to identify patient with upcoming primary care/cardiology appointments from which we will identify the patient and their corresponding clinician for whom to deliver the Alert or Email.

5.2 INFORMED CONSENT & PHI AUTHORIZATION PROCEDURES (OR DISCLOSURES)

Summary of Consent/HIPAA			
Activity		When	Rationale
Aim 1.			
Interview/ focus groups of clinicians	Informed consent	Prior to participation in activity	
Questionnaire	Waiver of documentation of informed consent	After nudge Email provided to all clinicians who received a nudge	The questionnaires will not be linked to any provider. No PHI/PII will be collected.
Veterans and Family Advisory Council	Waiver of documentation of informed consent		Only document linking subject to research is the consent document. No PHI/PII will be collected. The interaction will not be recorded, only notetaking.

	Aim 2.		
Collect baseline patient information and clinician prescribing activity: Identify actionable HF patient encounters and record baseline patient characteristics using CPRS/HF Dashboard / VINCI/CDW.	Waiver of consent, HIPAA waiver	Dates: Prior 12 months to nudge delivery	Need specific information on patients and corresponding clinician prescribing behavior
Create peer comparison reports based on prior prescribing history	Waiver of consent, HIPAA waiver	Dates: Prior 12 months to nudge delivery	Need specific information on patients and corresponding

using HF Dashboard and CDW.			clinician prescribing behavior
Deliver nudges (CPRS alerts and peer comparison emails) to clinicians	Waiver of consent	Dates: up to 90-day nudge delivery period	See justification below. Study could not be completed if consent required.
Review CPRS, HF Dashboard, and VINCI/CDW for clinician and patient outcomes in response to nudges	HIPAA waiver	Dates: up to 90 days after nudges delivered	Patient-level outcome data collection after HF nudges delivered

This section provides further detail on above table.

Aim 1: Interview/questionnaires, focus groups of clinicians.

Project information will be presented to the clinicians of Primary Care and Cardiology during a department meeting prior to pre- and post-intervention of the study. Also, all clinicians in Primary Care & Cardiology within SAVAHCs will receive invitation emails (contacted up to three (3) times) regarding the study. Those clinicians who would like to be interviewed and/or participate in the focus groups will contact the study team to begin the informed process. The clinician will be emailed the informed consent document and a meeting time will be arranged for its discussion. The informed consent process will occur via MS Teams where the study team member will discuss the project, provide time for the clinician to ask questions, then obtain consent should the potential subject agree to do so. The study team member will ask the potential subject to sign the consent via PIV certificate or ink signature and return to the study team. The signed consent will be stored within the VA secured study folder within the compliance binder.

After the intervention, the study team will present the next phase to the clinicians during staff meetings. Questionnaire link (REDCap) will be emailed to all the clinicians receiving the nudges after the 3-month nudge intervention was implemented to obtain feedback regarding the actual nudge. We are requesting a waiver of documentation of informed consent because the activity is minimal risk, and the participants are not under any obligation to provide his/her feedback. A started or completed questionnaire indicates his/her willingness to participate. We are requesting a waiver of documentation of consent based on the following rationale, which addresses the requirements for a waiver.

2a. The research involves no more than minimal risk to subjects.

It is common in daily life for VA clinicians to provide process feedback. The research presents no more than minimal risk of harm to subjects and involves no procedures for which written consent is normally required outside the research context. The short questionnaire utilizes standardized questions. The questions focus totally on the nudge(s) s/he had received. The Primary Care and Cardiology services have endorsed this study which is in line with their quality goals. The use of VA REDCap provides various layers of security for the data.

2b. The research could not be carried out practicably without the waiver or alteration.

The research outcomes are informative only when the results include clinicians' feedback to ensure process improvement. By including all clinicians who received nudges, there is a possibility that more will participate in a short <5 minute questionnaire. It is not practical to consent clinicians in Primary Care/Cardiology at all SAVAHCs facilities for a less than 5 minute questionnaire.

- 2c. The waiver or alteration will not adversely affect the rights and welfare of the subjects. VA clinicians commonly receive requests for feedback in daily clinical practice. There is no risk of penalties or consequences if they ignore the request to participate.

Aim 1. Veterans and Family Advisory Council

At the time of the Council meeting, the study team will review the written summary that embodies the elements of the ICF. All subjects will receive via Teams messaging an information sheet on the study. Subjects will be given the option of not participating. No PHI will be collected, and no recording will occur. We are requesting a waiver of documentation of informed consent because the activity is minimal risk and there is no physical contact with the subject.

Aim 2:

Collect baseline patient information and clinician prescribing activity.

We are requesting a HIPAA waiver to identify actionable HF patient encounters and record baseline patient characteristics using CPRS/HF Dashboard / VINCI/CDW. We will also use CDW/VINCI to develop peer comparison reports which display clinician prescribing activity. A waiver is required because although the study interventions are directed only at clinicians, we need to identify which patient encounters to target. Further, the study team is not directly interacting with patients and only passively collecting patient/clinician outcome data. Requiring informed consent to review PHI would make the study impossible to perform.

Aim 2. Deliver CPRS alerts and peer comparison emails to clinicians.

We are requesting a waiver of consent based on the following rationale, which addresses the requirements for a waiver.

2a. The research involves no more than minimal risk to subjects.

This is common in daily life for VA clinicians to receive CPRS reminders for recommended care, and therefore the study nudges are not different than those encounter in daily clinical practice. All of the recommendations follow established national and VA HF guidelines. The Primary Care and Cardiology services have endorsed this study which is in line with their quality goals.

2b. The research could not be carried out practicably without the waiver or alteration.

In real-world VA clinical practice, clinicians receive EMR/CPRS alerts that are delivered whenever there is an eligible patient encounter. It is critical that these nudges are therefore tested in the environment that would be utilized in clinical practice, i.e., to all clinicians. If clinicians are allowed to opt-out of receiving the study interventions (nudges), the objectives of the research could not be achieved. In other words, the research outcomes are informative only when the results demonstrate the effect on all clinicians, not only those who are interested in receiving nudges. By including all clinicians, this design will avoid an overly optimistic treatment effect in which nudges appear effective, that is, effective only for

those clinicians interested in receiving them. Conversely, if some clinicians do not respond to nudges or are dissatisfied with them, this knowledge would be important to know and would potential avoid wasteful or futile efforts to scale up nudge interventions in VA. In other words, we are testing nudges at the department / health system level, not to individual consenting clinicians.

2c. The waiver or alteration will not adversely affect the rights and welfare of the subjects.

VA clinicians commonly receive EMR / CPRS alerts and reminders in daily clinical practice. In this study, they are not obligated to follow any of these care recommendations; there is no risk of penalties or consequences if they ignore the nudges. Further, the study team will obtain clinician input via interviews/focus groups as well as Veteran input which could mitigate any unintended consequences and provide an opportunity to co-design the nudges.

2d. If the research involves identifiable private information or identifiable biospecimens, this research could not be carried out practicably without using the information/specimen in an identifiable form.

The research does not collect private information regarding the subjects (clinicians).

5.3 INCLUSION/EXCLUSION CRITERIA

Activity	Aim 1.
Interview, focus groups of clinicians	All clinicians in Primary Care and Cardiology
Veterans and Family Advisory Council focus group	All participants at Council meeting
	Aim 2.
Patient record review to deliver nudges (CPRS alerts and peer comparison emails) to clinicians	
Patients meeting these criteria:
 
Inclusion Criteria:
 
 • HF patient • Scheduled cardiology or primary care appointment • Not being prescribed SGLT2 or MRA class medication 
Exclusion Criteria:
 
 • eGFR < 20 ml/min/1.73m² or potassium > 5.0

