
Your patient has been identified in VA HF Dashboard as potentially eligible for an SGLT2 inhibitor. This alert is provided for informational purposes.
 
SGLT2 inhibitors are indicated in the 2022 ACC/AHA HF Guidelines (URL link provided) for patients with HFrEF (EF≤40%, NYHA class II-IV HF). Contraindications include urinary tract infection, eGFR < 25, type I diabetes.
 
Relevant data for this patient include: Prescription for beta blocker No prescription for ACE inhibitor LVEF 40% BNP 1550 Renal function: eGFR > 25
 
Suggested actions: Prescribe empagliflozin 10mg daily Alert primary care
 
If prescribing: Recommend checking renal function after starting therapy; reduce diuretic; watch for dehydration
	
Dear Dr. _____,
 
SAVAHCS Cardiology is working on new ways to help clinicians improve their patient's HF treatment. Based on AHA/ACC guidelines and the VA HF Dashboard, you have patients who could be on an SGLT2 inhibitor but have not been prescribed one.
 
Among eligible patients, your rolling 90-day SGLT2 prescribing rate: XX% [one of the following] Average of your peers at SAVAHCS: XX% Your top performing peers at SAVAHCS: XX%
 
If you have any questions, please email study coordinator XXX
 
Sincerely, XXXX Clinical Research Coordinator XXXX Study Principal Investigator

Focus group with SAVAHCS Veteran and Family Advisory Council

[figure not shown]
We will meet twice virtually with the Advisory Council during the study. We will ask for their feedback on their perceptions of study benefit and any suggestions for improvement. Unlike the other focus groups and interviews with clinicians, we will only take notes, but no audio

recording will occur. We will not ask for any individually identifiable information, only general feedback on the study.

Aim 2. NUDGE EFFECTIVENESS

Table 2. Study design			
	Peer comparison		
		Yes	No
Informational alert	Yes		
	No		

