Informational Alert (in CPRS) and Peer Comparison Email for clinicians. (See Figure 1 above) During department meetings and by email, Primary Care and Cardiology clinicians will be notified about the goals of the study and will receive education on HF treatment guidelines to encourage optimal standard of care at baseline. Over the next 3 months, we will measure baseline rates of prescribing (SGLT2, MRAs); this will serve as control (pre-intervention period). Next, during the 3-month intervention period, clinicians will receive ‘nudges’ per their assignment to one of four groups. Those in the usual care arm will receive no other interventions. Clinicians in the alert only arm will receive an alert approximately two business days prior to a patient’s upcoming appointment. Clinicians will receive approximately one to two alerts per week or less. Clinicians assigned to peer comparison only, will receive messages by unencrypted email approximately every two weeks or even less often regarding their SGLT2i and MRA prescribing performance relative to their peers. We will review their prescribing activity for HF patients using VINCI/CDW data from the prior 12 months in order to generate these peer comparisons. Emails will be unencrypted because there is no PHI/PII. The clinicians in the combined alert and peer comparison arm will receive both interventions. All alerts and emails are based on HF patient data from VA PBM HF Dashboard, an operational/quality improvement dashboard available to all VA clinicians (https://vaww.pbi.cdw.va.gov/PBIRS/Pages/ReportViewer.aspx?/GPE/PBM_AD/SSRS/HeartFailure/HF_Dashboard) but most heavily utilized by pharmacists. (See sample screen from HF Dashboard below – no PHI)

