8.0 DATA ANALYSIS & STATISTICAL CONSIDERATIONS

Power calculation. One study reported a 14% absolute increase in beta-blocker prescription with enhanced alert compared to usual alert/usual care. Another reported a 7% absolute increase in new prescription of any GDMT in 30 days, also driven by beta-blocker. We anticipate a 5% absolute increase in new prescriptions (SGLT2 or MRA) per intervention arm, compared to usual care. We are anticipating a lower treatment effect because SGLT2 inhibitors are newer, potentially seen as requiring interdisciplinary collaboration, and MRAs require serial lab monitoring. To detect this difference with an 80% power and alpha of 0.05, a sample size of 168 patients who are eligible to activate the alert are required in each treatment group, for a total study sample size of 672 patients encounters. We anticipate that we can achieve this number of patient encounters across the approximately sixty participating clinicians including any possible attrition.

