Data Analysis. Though randomization occurs at the clinician level, we will measure outcomes at the patient level. The dataset used for analysis will be limited to all MRA- and SGLT2i-eligible identified in the HF dashboard (this includes patients in the control group-- even though no alert will be generated). This sample allows us to compare differences in rate of prescription of the same patient types between the three intervention groups and control group. Descriptive statistics will comprise patient and provider demographics, including practitioner specialty and type, and part-time status. General Linear Models (GLM) and chi square tests will be used to compare continuous and categorical demographic variables, respectively, between the three interventions and control groups. Significant differences will be defined with p values < 0.05. Generalized Linear Mixed Models (GLMM) will be used to compare rates of both SGLT2 or MRA (in separate, univariate analyses) between the nudge intervention and control groups. Practitioner specialty and type, part time status, years of experience, and patient visit number will be included as covariates, and the patient, clinician, and clinic assignment (clustering of providers), will be entered as random effects. While these covariates are strata for randomization, it is unlikely, due to the study sample size, that all combinations will be equally distributed between the two groups. We will therefore need to employ statistical control of these potential influences. The GLMMs will be specified as random coefficient models or growth curve models to evaluate changes in prescription behavior over time, as well as between groups. Models will include the preintervention baseline as a covariate and will use all patient visits until the conclusion of the data collection period. Significant differences will be concluded with odds ratio and 95% confidence intervals that do not contain the value 1.0. This statistical approach

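### No date fixes eligibility for the analysis set, and if that set follows the rolling visit-linked screen, the peer email's effect can be understated

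*Combined protocol and SAP*

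**What the plan says.** Section 5.3 gives the only patient criteria for Aim 2, in a row about reviewing records in order to deliver nudges. They include "Scheduled cardiology or primary care appointment" and "Not being prescribed SGLT2 or MRA class medication". Section 5.1 gives the timing as "Daily review of VA PBM dashboard", and Section 5.4.1 has the coordinator find eligible encounters by those same criteria.

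The two nudges are timed differently in Section 4.3. A clinician in the alert arm "will receive an alert approximately two business days prior to a" patient's visit. The email goes out about every two weeks or less often and reports the clinician's overall prescribing. Its prototype says "you have patients who could be on an SGLT2 inhibitor but have not been prescribed one", which concerns the whole panel and no particular visit. Section 5.1, however, also describes the appointment screen as the source "from which we will identify the patient and their corresponding clinician for whom to deliver the Alert or Email".

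In Section 8.0 the power paragraph states that "168 patients who are eligible to activate the alert are required in each treatment group", and totals these as 672 encounters. The analysis paragraph says "The dataset used for analysis will be limited to all MRA- and SGLT2i-eligible identified in the HF dashboard", adds that control patients are included although no alert is generated for them, and bases the models on patient visits. It gives neither an appointment condition nor an index date.

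**The concern.** Untreated status is an entry condition that the email is meant to change. Suppose a patient's first visit in the nudge period is in week 8, an email reaches the clinician in week 2, and the clinician prescribes in week 3. A screen run shortly before the visit finds the patient already treated and passes over them. The email's success is then missing from both numerator and denominator. An alert-prompted prescription is not lost in this way, because the alert is sent only after the screen has identified the patient.

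The exposed contrasts are ones the plan cares about. Section 2.0 hypothesises that each nudge beats usual care and that the combination beats either alone, and Section 1.0 asks which of the three is most effective. A weak email result, or an apparent lack of benefit from adding the email to the alert, could come partly from how patients enter the dataset.

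**Working it through.** **1. The plan's own figure.** 4 × 168 = 672 reproduces. The 168 cannot be reproduced, because no usual-care rate is stated. For a 5-point difference at 80% power and two-sided alpha 0.05, the pooled two-proportion formula gives 167 per group at a usual-care rate of 0.25% and 435 at 5%. That is a separate matter, and this point does not rest on it.

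**2. Which analysis set does the text describe?**
- Towards a rolling, alert-triggered set: the daily review (5.1), the encounter-by-encounter screen (5.4.1), sizing on patients who could activate the alert (8.0), and the remark that controls are included although they generate no alert (8.0).
- Towards a fixed or wider set: the 5.3 row concerns nudge delivery, and the 8.0 dataset sentence carries no appointment condition.
- Missing under either reading: a date before the first nudge on which untreated status is read.

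**3. Size if the rolling screen defines the set.** Inputs:
- True email effect of 5 points: Section 8.0.
- Usual-care rate p0 of 5%, 10% or 19%: assumed. The top value equals the starting figure of the alert trial cited in Section 1.0, which had a different endpoint.
- f, the share of the email's effect that occurs before the screen: not in the documents, so varied.

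The screened-out patients leave numerator and denominator, so

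measured email rate = (p0 + 0.05 − 0.05f) / (1 − 0.05f).

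Example, p0 = 10% and f = 25%: (0.15 − 0.0125) / (1 − 0.0125) = 0.1375 / 0.9875 = 13.92%, which is 3.92 points above usual care.

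| f | p0 = 5% | p0 = 10% | p0 = 19% |
|---|---|---|---|
| 0% | 5.00 | 5.00 | 5.00 |
| 10% | 4.55 | 4.57 | 4.62 |
| 25% | 3.86 | 3.92 | 4.04 |
| 50% | 2.69 | 2.82 | 3.05 |

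(Measured email-minus-usual-care difference, percentage points.)

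In patients: the email would add 168 × 0.05 = 8.4 prescriptions per group. Of these, 2.1 disappear at f = 25% and 4.2 at f = 50%.

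**4. Against the alert.** If the alert's true effect is also 5 points and none of it is lost, the measured email-minus-alert difference is −1.14 to −0.96 points at f = 25% and −2.31 to −1.95 at f = 50%, when the true difference is zero.

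**5. Robustness.** Background prescribing before the screen would also be removed, in every arm. Removing 10% or 25% of it throughout leaves the measured email effect at 3.9 to 4.2 points for f = 25% and 2.7 to 3.1 for f = 50%, so the picture hardly changes.

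**6. Fixed cohort.** If untreated status is read once before any nudge and all later prescriptions count, f = 0 by construction and this bias is zero.

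**The case against.** A reader might infer that email-triggered prescriptions do drop out and that the email-versus-alert comparison is therefore biased. The documents do not establish this, for five reasons.

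- The 5.3 criteria are labelled for nudge delivery, and Section 8.0 defines the analysis set separately. Section 4.2 lists 1400 patients for analysis, which fits a set wider than 672 alert-triggering encounters. A fixed-cohort reading remains open.
- Section 5.1 ties delivery of the email, like the alert, to the appointment screen. This may narrow the timing gap, although an email about the whole panel can still prompt prescribing for a patient who is screened later.
- Data run from 12 months before baseline to after the nudges (5.4.2), and the models include a baseline. An eligible patient identified in the pre-period could already be in the data. This helps only if such patients are kept in the set, which the plan does not say.
- f may be small. The email names no patient, so acting between visits means searching for candidates, and Section 8.0 itself notes laboratory monitoring and shared responsibility as barriers. At f = 10% the loss is under half a point.
- Section 8.0 specifies nudge versus control, and no email-versus-alert test is defined.

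It is also tempting to assume that only prescriptions written at visits count, which would make the loss larger. No section limits the outcome in that way.

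These arguments make the concern conditional and leave its size open. They do not supply the missing date, and most of the operational text still points to the rolling screen.

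**Conclusion.** The concern holds conditionally. The plan fixes no date before the first nudge for eligibility in the analysis set, and the screen it describes reads untreated status at a time when the email may already have changed it. If the analysis set follows that screen, the bias runs against the email: versus usual care, in its contribution to the combined arm, and hence in any comparison with the alert. Of a true 5 points, about 3.9 to 4.0 would be measured at f = 25% and 2.7 to 3.1 at f = 50%.

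These figures illustrate the range and are not estimates of what will happen. They rest on the assumed usual-care rates, on an f that the documents do not give and, for the alert comparison, on alerts not prompting prescriptions for the clinician's other patients before their own screen. The stronger statement, that the email-versus-alert result is biased as planned, is not supported.

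**What to change.** In Section 5.3, state that the appointment rule triggers nudge delivery only. In Section 8.0:

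- Define the analysis cohort from one dashboard/CDW extract on day 1 of the intervention period, before any nudge: patients of randomised clinicians who meet the eligibility criteria and are untreated on that date. Say whether untreated means on neither class or missing at least one, since the present criterion can be read either way.
- If a visit condition is wanted, use appointments already scheduled on day 1.
- Count every new SGLT2 or MRA prescription from day 1, whether or not it is written at a visit, and say how the visit-based model records one written between visits.
- Keep the rolling visit-based set, including later-booked visits, as a sensitivity analysis.

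The cost is one dated extract from sources that the HIPAA waiver in Section 5.2 already covers, plus the wording changes. With a visit condition, later-booked visits leave the main cohort, so its count should be checked against the planned 672 encounters. If a fixed cohort was always intended, a sentence giving its date and counting all later prescriptions settles the matter.
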